9.1. Methods Used to Minimize Bias and Maximize Validity

This study will be randomized using CONSORT guidelines stated below (www.consort-statement.org). The randomization will be conducted via sealed envelope. The specific randomization will be discussed in further detail below.

CONSORT 2010 Flow Diagram

10. Subject Selection

10.1. Screening

All subjects who are indicated for a medically necessary Single Lumen PICC line will be screened for eligibility for the study.

10.2. Consent

If the patient is interested in moving forward with this study, then they will sign the study informed consent. Those who do not consent will be logged as “declined to participate” in the screening log. Those who consent will be screened by the site staff using the inclusion and exclusion criteria.

10.3. Inclusion Criteria

- 1) Patient is indicated for a medically necessary PICC for therapeutic delivery medication
- 2) Patient is eligible to receive a single lumen PICC
- 3) Patient is an adult prescribed a PICC line
- 4) Patient’s expected duration of treatment requiring a PICC for a minimum of 16 days post device implantation
- 5) Patient understands and is willing to comply with all study requirements and has voluntarily signed the Informed Consent Form (ICF).

10.4. Exclusion Criteria

- 1) Is pregnant, lactating, or is planning to become pregnant during the time of the study
- 2) Has been previously enrolled in this post market clinical evaluation, or is participating in another clinical study that is contraindicative to the treatment or outcomes of this investigation
- 3) Venous thrombosis in any portion of the vein to be catheterized
- 4) Conditions that impede venous return from the extremity such as paralysis or lymphedema after mastectomy
- 5) Orthopedic or neurological conditions affecting the extremity
- 6) Anticipation or presence of dialysis grafts or other intraluminal devices, including pacemakers, within a month of patient enrollment start
- 7) Patients who are on anticoagulation therapy prior to the study (10-14 days). *Note: (If patients are placed on anticoagulation (low dose) therapy while hospitalized, these patients are allowed.)*
- 8) Patient has relinquished control of care to a guardian and/or facility
- 9) Patient has any significant medical or physical condition that, in the opinion of the PI, would make the subject unsuitable for participation in the post market clinical evaluation
- 10) Inability to complete the protocol in the opinion of the clinical staff due to safety or other reasons

10.5. Randomization

After consent and review of the inclusion/exclusion criteria, the Investigator can assign a randomization prior to baseline ultrasound. If during the ultrasound procedure, the subject meets an exclusion criterion, then this subject will be considered a screen fail.

[figure not shown]

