Exclusion Criteria:	
 1) Is pregnant, lactating, or is planning to become pregnant during the time of the study 2) Has been previously enrolled in this post market clinical evaluation, or is participating in another clinical study that is contraindicative to the treatment or outcomes of this investigation 3) Venous thrombosis in any portion of the vein to be catheterized 4) Conditions that impede venous return from the extremity such as paralysis or lymphedema after mastectomy 5) Orthopedic or neurological conditions affecting the extremity 6) Anticipation or presence of dialysis grafts or other intraluminal devices, including pacemakers, within a month of patient enrollment start 7) Patients who are on anticoagulation therapy prior to the study (10-14 days). Note: (If patients are placed on anticoagulation (low dose) therapy while hospitalized, these patients are allowed.) 8) Patient has relinquished control of care to a guardian and/or facility 9) Patient has any significant medical or physical condition that, in the opinion of the PI, would make the subject unsuitable for participation in the post market clinical evaluation 10) Inability to complete the protocol in the opinion of the clinical staff due to safety or other reasons
Study Duration:	
Enrollment is expected to take about 2 months.
 
Data collection completed when Last Subject Last Visit occurs. (Calculated by date of procedure + 12 days for the last subject)

Reported Adverse Event Data:	Product observations and adverse events will be collected and reviewed per
	[REDACTED] (product complaints). Additional safety evaluations will be
	performed if needed.

Schedule of Activities

Subject Timepoints	Visit 1 Screening (- 7 days)*	Visit 2 Procedure (0 day)	Visit 3 7 day evaluation (± 5 days)	Visit 4 14 day evaluation and End of Study (± 7 days)***	Unscheduled visits (as needed)
ICF	X				
Inc/Ex criteria	X				
Medical History	X				
Demographics	X				
Con Meds	X	X	X	X	X
Labs (specific per protocol and standard of care)	X	X	X	X	X
Randomization	X**	X**			
Surgical Summary		X			
Ultrasound (as needed per DVT, AND at these specific timepoints)			X	X	X
AE/SAEs		X	X	X	X
Follow up form/unscheduled visit form			X	X	X
End of study forms				X	

*Screening can happen on the same day of the procedure. Screening can also happen 7 days prior to the procedure.

**Randomization can occur at screening or prior to procedure.

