8.1. Study Overview

This post market clinical evaluation is a prospective, randomized post-market assessment. Each eligible subject will receive a single lumen PICC device and will be placed per the manufacturer's IFU and in accordance with institutional policy.

Per institution policy, due to the fact that the HydroPICC is not a standard of care device, the patient will be consented prior to insertion. This consent will follow the institution's standard of care policies.

any patient receiving a single lumen PICC will be approached to join this study. After the patient consents, and the site reviews the inclusion criteria, the subject can be randomized.

Screening data will be reviewed to determine subject eligibility. Subjects who meet all inclusion criteria and none of the exclusion criteria will be entered into the study. There is an exclusion criteria which requires an ultrasound, and a subject can still be screen failed at the time of insertion.

The following treatments will be used:

AVI device: Access Vascular HydroPICC Single Lumen PICC

Comparator device: [REDACTED] Single Lumen PICC

Vein: Preference is Basilic Vein followed by Brachial Vein, then Cephalic Vein

Once a subject is inserted with a PICC line, they are considered enrolled.

Total duration of subject participation will be the duration for which the catheter is indwelling in the patient up to 16 days. The total study duration is expected to not exceed 23 days, including procedural pre-screen. Insertion of the PICCs will be prioritized with the following: Basilic vein then Brachial vein followed by Cephalic vein. Diagnosis of both asymptomatic and symptomatic vein thrombosis will be established by Doppler ultrasound examination. Examinations will be performed prior to device insertion to establish patient baselines.

[figure not shown]
Ultrasound will be performed pre-insertion of the device, at 7 days post-insertion (± 5 days) and 14 days (± 7 days). Data will be collected using a scale defined previously.

9. Study Methods and Measurements

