14.1. Screening Visit (Visit 1)

1. Assign the subject a unique screening number.
2. Perform informed consent process; subjects to sign and date the Informed Consent Form.
3. Record demographics data.

4. Record medical history, including a history of condition(s) requiring chemotherapy or antibiotics, diagnosis date, and prior treatments related to the relevant condition(s).
5. Record baseline labs, if available.
6. Perform a complete physical examination.
7. Perform and record vital signs.
8. Schedule subject for Procedure visit in no more than 5 days
9. Randomize the subject

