16.3. Analysis Populations

The primary analysis will be based on a Full Analysis Set (FAS) analysis population defined as those who were randomized and met all inclusion and exclusion criteria. A Per-Protocol (PP) population will be completed that excludes subjects who have one or more major protocol deviations. Major protocol deviations will be identified prior to locking the database for the final analysis and will include, but are not limited to, not receiving the randomized treatment, not completing the study, and not have met all inclusion and exclusion criteria. Information for subjects not in the FAS population will be listed if available.

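### The open-label arm may be assigned before the baseline ultrasound that settles exclusion 3, and randomized subjects who then fail it leave the primary analysis set

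*Combined protocol and SAP*

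**What the plan says.** **When the arm is assigned.** Section 10.5 says that, after consent and review of the entry criteria, "the Investigator can assign a randomization prior to baseline ultrasound". Section 14.1 lists "Randomize the subject" as step 9 of Visit 1, just after step 8, "Schedule subject for Procedure visit in no more than 5 days". The Schedule of Activities says "Randomization can occur at screening or prior to procedure". It allows screening on the day of the procedure or up to 7 days before it.

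**When exclusion 3 is settled.** Section 8.1 says: "There is an exclusion criteria which requires an ultrasound, and a subject can still be screen failed at the time of insertion". Section 14.2 step 3 places the scan at Visit 2, before the assigned catheter goes in, and allows the subject to be failed there.

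**How much judgement is left.** Section 8.1 gives an order of veins: "Vein: Preference is Basilic Vein followed by Brachial Vein, then Cephalic Vein". Section 13.7 bases the diagnosis on any of three ultrasound signs and has scans with poor visualization recorded as indeterminate. Section 12.2 states that there is no blinding.

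**What happens to a subject who fails.** The FAS, used for the primary analysis, is "defined as those who were randomized and met all inclusion and exclusion criteria" (section 16.3). Under section 10.6 only demographics and the reason for failure are kept, and a second envelope set supplies the replacement. Section 16.3 adds: "Information for subjects not in the FAS population will be listed if available".

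**The concern.** Randomization protects the comparison only if the decision to keep a subject cannot depend on the arm. Here the arm can be known for up to 5 days (section 14.1) or 7 days (Schedule of Activities) before the last eligibility decision. That decision concerns the state of the vein, which plausibly predicts the thrombosis endpoint. If borderline scans were handled differently in the two arms, venous risk at baseline would differ between the groups analysed.

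A different analysis set would not repair this. A subject failed at Visit 2 never receives a study catheter, so there is no later endpoint to restore. Protection has to come from the order of the steps.

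What is at stake is the between-arm comparison in section 16.5.1 (trend test and Fisher's exact test), not the feasibility aim in section 16.2.

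**Working it through.** **The plan's own figure.** Section 10.7 gives 10 analysed per arm plus 4 extra: 2 × 10 + 4 = 2 × 12 = 24, as stated. It does not come from a power calculation, and nothing below changes it.

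**The sequence.**
1. Assignment is permitted before the scan (10.5; 14.1 step 9; Schedule).
2. The scan settles exclusion 3 at Visit 2 (8.1; 14.2 step 3).
3. The arm is not masked (12.2).
4. A subject failed at that point leaves the FAS (16.3) and is replaced (10.6).

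Section 10.5 has the other criteria reviewed before assignment, so the gap is confined to exclusion 3. Two judgements within it have no rule: whether an indeterminate scan meets the exclusion, and when to move to the next vein and when to fail the subject.

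**Size, for illustration only.** The documents give no frequency of baseline thrombosis, indeterminate scans or screen failure, so every input is assumed. There is no device effect. A share p of candidates has event risk h, the rest have risk l, and a fraction s of the high-risk candidates is failed in one arm only and replaced.

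- Overall rate: r = p·h + (1 − p)·l
- High-risk share left in the affected arm: m = p(1 − s)/(1 − p·s)
- False difference: r − [m·h + (1 − m)·l] = (h − l)(p − m)

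Example with p = 0.3, h = 0.70, l = 0.40, s = 0.50: r = 0.21 + 0.28 = 0.490; m = 0.15/0.85 = 0.1765; difference = 0.30 × 0.1235 = 3.71 points.

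| p, h, l | r | s = 0.10 | s = 0.25 | s = 0.50 |
|---|---|---|---|---|
| 0.3, 0.70, 0.40 | 49.0% | 0.65 | 1.70 | 3.71 |
| 0.2, 0.70, 0.45 | 50.0% | 0.41 | 1.05 | 2.22 |
| 0.3, 0.80, 0.35 | 48.5% | 0.97 | 2.55 | 5.56 |

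Differences are in percentage points. The overall rates were set near the 48.82% cited in section 5.2.

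**One subject.** Replacing one high-risk candidate by a random one in an arm of 10 shifts the expected rate by (h − r)/10: 2.1, 2.0 and 3.15 points for the three rows.

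**Against sampling error.** At 10 per arm and a 49% rate, SE = √(2 × 0.49 × 0.51/10) = 22.4 points and 1.96 × SE = 43.8 points. The largest shift in the table is 5.56/22.4 = 0.25 of one standard error.

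**Effect on the test.** For the first row, by exact enumeration of the two-sided Fisher test (10 per arm, p ≤ 0.05), the chance of a significant result favouring the affected arm is 0.64% at s = 0, 0.69% at s = 0.10 and 1.00% at s = 0.50.

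**Harsher assumptions.** With 20% to 30% of candidates at 80% risk and 25% to 100% of them failed in one arm only, the false difference is 1.6 to 13.4 points at an overall rate of 48.82%, and 2.2 to 17.8 points at 38.5% (the other rate cited in section 5.2). The top value has p = 0.3 and l = (0.385 − 0.24)/0.7 = 0.207, so failing all high-risk candidates gives 38.5 − 20.7 = 17.8 points. Two-sided Fisher rejection reaches at most 4.7%, from about 1.3% with no selection.

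**The case against.** The strongest reply has five parts.

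- **Assignment before the scan is optional, and screening may fall on the procedure day.** True, but the Visit 1 list includes randomization and nothing requires the scan to come first.
- **Little discretion remains.** Failure requires an exclusion criterion to be met, thrombosis is defined by three signs, and an indeterminate scan arguably establishes none of them. That narrows the gap. It is still an inference the protocol does not state, and the choice between changing vein and failing the subject stays open.
- **Failures will be seen.** Section 16.1 has summaries by randomized group, section 16.4 summarizes completion and discontinuation, section 10.6 records the reason, and section 9.1 plans a CONSORT diagram. None of the readable text names randomized screen failures as something to report by arm, so visibility is partial.
- **Details may lie elsewhere.** Section 12.1 mentions a match-and-replace method and defers the assignment methodology to the Statistical Analysis Plan. Section 16 as supplied does not describe it, and some figures are not shown. Such text could add detail but could not undo sections 10.5 and 14.1.
- **This is an unpowered pilot not meant to support claims** (sections 8 and 16.1). That stands and limits the consequence. The protocol nevertheless plans between-arm tests, and a larger study could inherit the sequence.

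The size is also driven by assumption, as the spread between the two sets of scenarios shows.

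**Conclusion.** The concern holds. As written, the plan lets the final eligibility decision be made with the arm known, and subjects failed at that point leave the primary analysis set. This shows that selection is possible, not that it occurred. On moderate assumed inputs the false difference is about 0.4 to 5.6 points; on harsher ones it reaches 17.8. The moderate values are at most a quarter of the 22.4-point standard error, and the Fisher test stays below 5% in every scenario tried, so the main exposure is bias in the estimate. The point should be fixed because the weakness is avoidable at very little cost, not because the numerical effect is large.

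**What to change.** 1. Remove randomization from section 14.1 step 9 and from the screening column of the Schedule of Activities.
2. In sections 10.5 and 14.2, open the next sealed envelope only once the baseline ultrasound and all entry criteria are recorded and signed off, immediately before insertion.
3. State in advance, in section 10.5 or 13.7, how an indeterminate baseline scan counts for exclusion 3.
4. In sections 10.6 and 16.3, record the assigned arm and report any remaining exclusions after randomization by arm, with reasons.

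Ultrasound failures after assignment then fall to zero by construction, and the second envelope set is no longer needed for them. Choosing a vein or failing a subject would also be settled before the arm is known. Replacement of discontinued subjects (section 11) and the target of 10 per arm can stay. One caution: if matching in section 12.1 means same-arm replacement, which the documents do not say, a replacement's arm would be known in advance whatever the envelope timing. The randomization description should settle this.

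**Cost:** one short amendment, with no extra procedure or subjects. Assignment moves to Visit 2, which the Schedule already allows. Both PICC kits must be at hand at insertion.

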10.6. Screen Failures

Any subject who signs an informed consent but fails to meet the required entry criteria is considered to be a Screen Failure. Screen Failure subjects will have their demographic information captured in the appropriate CRF with the reason for screen failure specified. No other information will be collected or analyzed. Since this is a pilot study, the analysis will be conducted on 10 subjects on each arm. If a

[figure not shown]
screen failure occurs, the investigator will need to continue to consent, randomize, and enroll until the 10 subjects for each arm is completed. A second set of randomization envelopes will be used for the recruitment of these screen failed subjects.

10.7. Enrollment

A subject is considered enrolled when the assigned PICC is inserted. Due to the current situation with COVID, the sponsor is concerned about lost to follow up rates. To prepare for this, the site will enroll 4 extra subjects bringing the total to 24. The plan is to analyze 10 enrolled subjects on each arm, but the site will recruit for 12 in case of COVID related follow up issues.

Screening process

A Prospective, Randomized PICC Asymptomatic Thrombosis Study (PROPATH)	Number: 20-002 Version: C 28Apr2021 Page: 17 of 30
---	---

11. Discontinued Subjects

If a subject is unable to complete the study for any reason, then the investigator will use the screen failed randomization envelope to recruit for this discontinued subject. Data from the discontinued subject will not be used for the per protocol analysis. However, demographics will be used for the recruitment analysis. Any subjects in section 12 described below will be replaced using the method mentioned in this paragraph.

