14.2. Surgical Visit- (Visit 2)

1. Perform and record vital signs.
2. Record labs, if available.
3. Conduct Ultrasound prior to insertion of the assigned PICC. Screen fail if necessary.
4. Insert device per assigned randomization, IFU, and institutional procedures.
5. Confirm patient entry into study.
6. Take picture of insertion site.
7. Record adverse events (if any).

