16.5.3. Analysis of Other Endpoint(s)

Failure and safety endpoints will also be compared between the HydroPICC group and control group using Fisher's exact tests.

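### Sections 8.1 and 10.7 define enrolment differently, and 10.7 ties the analysed subjects to placement of the assigned device while 16.3 bases the primary analysis on randomization and eligibility

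*Combined protocol and SAP*

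**What the plan says.** All references are to the combined protocol and SAP.

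- **Section 8.1** (Study Overview): "Once a subject is inserted with a PICC line, they are considered enrolled". The device is not tied to the assignment.
- **Section 10.7** (Enrollment): "A subject is considered enrolled when the assigned PICC is inserted". The same section adds that "the site will enroll 4 extra subjects bringing the total to 24", and then: "The plan is to analyze 10 enrolled subjects on each arm, but the site will recruit for 12".
- **Section 10.6** (Screen Failures): "the analysis will be conducted on 10 subjects on each arm". A screen failure is a consented subject who does not meet the entry criteria; an unsuccessful placement is not covered.
- **Section 14.2** (Visit 2): after the baseline ultrasound and insertion of the device per randomization, the next step is "Confirm patient entry into study". This order fits 10.7.
- **Section 10.5**: randomization can take place before the baseline ultrasound, and so before insertion.
- **Section 16.3**: the primary analysis uses the FAS, meaning everyone randomized who satisfied the entry criteria. Getting a device other than the randomized one is a major deviation that removes a subject from the per-protocol (PP) set only.
- **Section 16.1**: summaries are by randomized group, and percentages use subjects whose result is not missing.
- **Section 16.5.3**: "Failure and safety endpoints will also be compared between the HydroPICC group and control group".

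**The concern.** Whether the assigned catheter can be placed becomes known only after randomization, and it may depend on the device. If that result decides who counts as an analysed subject, the arms compared are no longer the arms that were randomized. Difficult placement could plausibly go with vein injury, and Section 5.2 names endothelial injury as one of three contributors to venous thrombosis, so the loss need not be neutral for the primary endpoint.

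There is also a practical gap. The site may take a subject who is not enrolled under 10.7 to be outside the follow-up schedule. Section 8.1 ties the length of participation to the time the catheter is indwelling, but no section says whether a switched subject attends Visits 3 and 4. Such a subject could be in the FAS by definition, have no ultrasound result, and so leave the denominator that 16.1 prescribes. The FAS would then shrink in practice to the group that 10.7 describes. With 10 analysed per arm, one subject can matter.

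**Working it through.** **1. The plan's own figure.** Section 10.7: 2 × 10 + 4 = 24, and 24 / 2 = 12 per arm. The figure reproduces. The implied allowance is 4 / 24 = 16.7%, and 10.7 gives COVID-related follow-up loss as its reason. Section 16.2 states that there was no power analysis, so there is no power figure to check.

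**2. Status of an eligible, randomized subject under each section.**

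| What happens at Visit 2 | Enrolled, 8.1 | Enrolled, 10.7 | Screen failure, 10.6 | FAS, 16.3 | PP, 16.3 |
|---|---|---|---|---|---|
| Assigned PICC inserted | yes | yes | no | yes | yes, if no other major deviation |
| Other PICC inserted | yes | no | no | yes | no |
| No PICC inserted | no | no | no | yes | no |

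Sections 8.1 and 10.7 disagree only in the second row. Section 10.7 (analyse enrolled subjects) and 16.3 (analyse randomized, eligible subjects) disagree in the second and third rows.

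**3. How often this could arise.** The documents give no rate, so f below is an assumption. It covers every way the assigned device may fail to go in, both a switch and no PICC at all.

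Expected number among 12 in an arm = 12f. Chance of at least one = 1 − (1 − f)^12.

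- f = 5%: 0.6 expected; 1 − 0.95^12 = 46%
- f = 10%: 1.2 expected; 1 − 0.90^12 = 72%
- f = 15%: 1.8 expected; 1 − 0.85^12 = 86%

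Across all 24, with 1 − (1 − f)^24, the chances at 5%, 10% and 15% are 71%, 92% and 98%. At 2% the chance is 38%.

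**4. What one subject can do.** The counts are hypothetical; the test is the two-sided Fisher's exact test of 16.5.1.

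- Subjects with the assigned device only, 0/10 v 5/10: each extreme table has probability C(10,5) / C(20,5) = 252 / 15,504, so p = 2 × 252 / 15,504 = 0.033.
- One further randomized subject, with thrombosis, kept in the first arm, 1/11 v 5/10: the tables no more likely than the observed one sum to (2,772 + 210 + 462) / 54,264, so p = 0.063.

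The choice of rule can therefore move a result across the 0.05 threshold of 16.1. If the further subject is in the FAS but is never scanned, the table falls back to 0/10 v 5/10.

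**The case against.** The best defence is that the analysis set is already settled. Section 16.3 governs the primary analysis and has no enrolment or insertion condition, 16.1 summarizes by randomized group, and 16.3 foresees a subject who does not get the randomized device. This stands against a stronger reading that a reader might infer, namely that these subjects drop out of the primary analysis: as 16.3 defines that analysis, they do not. It does not remove the conflict, because 10.6 and 10.7 also say who will be analysed and give a different answer.

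A reader might also infer that 8.1 and 10.7 treat failed placements differently. They do not. With no PICC inserted, the subject is enrolled under neither; only a switch of device separates the two sections. The wording of 8.1 may be shorthand, since it follows a list of the two study devices and 14.2 calls for insertion per assignment.

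A third tempting reading is that failed placements vanish from the failure comparison in 16.5.3. The documents do not show this. The endpoints under 7.3 are not visible, so placement failure may or may not already count, and 16.5.3 does not restrict itself to enrolled subjects. Adverse events are collected from the procedure onward (15.2), so placement problems have a recording route.

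On follow-up, 11.1 asks that discontinued subjects be encouraged to complete their remaining visits. Whether this reaches someone who never counted as enrolled is unclear. The CONSORT diagram and the screening-process figure are not shown in the text available and may say more.

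Finally, this is an unpowered pilot that, by 16.1, is not meant to support claims. That limits the weight of the point but does not settle which rule applies.

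**Conclusion.** The point holds as a conflict between sections. Section 8.1 and 10.7 disagree on a subject who receives the other device. Section 10.7, with the matching sentence in 10.6, disagrees with 16.3 on both that subject and one in whom no PICC is placed. Following 10.7 would select the analysed subjects on a post-randomization device result; following 16.3 would not, but leaves open whether a switched subject is scanned and how a subject without a PICC is reported.

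The number affected is small in absolute terms: 0.6 to 1.8 expected per arm of 12 at assumed rates of 5% to 15%. At those rates at least one case in an arm has a chance of 46% to 86%. The rates are assumptions and include failed placements as well as switches, so they overstate how often 8.1 and 10.7 differ. The Fisher example shows sensitivity only and predicts nothing. The planned total of 24 is unaffected. No conclusion is drawn about 16.5.3. For a pilot this is a moderate point, worth correcting because the repair is cheap and the selection could not be undone once follow-up had been missed.

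**What to change.** 1. Use one enrolment definition in 8.1, 10.7 and 14.2.
2. Reword 10.7, and the matching sentence in 10.6, so that 10 per arm is a recruitment target for completers. State that membership of the primary analysis follows 16.3: all randomized, eligible subjects, by assigned arm, whatever device was inserted.
3. State that a subject who receives a device other than the assigned one still has the Visit 3 and Visit 4 ultrasounds and is analysed in the assigned arm.
4. Report randomized, eligible subjects with no PICC placed, by arm, as placement failures without an ultrasound outcome. The endpoint is read on the vein carrying the PICC (13.7), so they have no defined scan result, but they should be visible in the accounting.
5. Keep replacement under Section 11 for recruitment if wished, and state that it does not remove the replaced subject from the FAS.

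The cost is protocol wording plus follow-up of perhaps 1 to 3 subjects on the existing visit schedule. The downside is that a few FAS subjects may not carry the assigned device or may lack an ultrasound result; the PP set in 16.3 already excludes subjects who did not receive the randomized device.
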